• Positive and Negative Syndrome Scale (PANSS) (Kay et al. 1987), a rater-based scale used to assess and measure the severity of psychiatric symptoms over the past one week (unless previously obtained within the last one week)

The screening visit will take approximately two hours to complete and may be divided into separate sessions to minimize participant fatigue.

Research Laboratory Measures

Samples for these measures will be obtained at visit 2 (week 0), the start of the placebo run-in phase, and other time points as noted below.

- Blood sample (approximately 20 ml) to measure levels of immune markers and antibodies to infectious agents including high sensitivity CRP, TNF alpha, antibodies to food antigens such as casein and gliadin (Severance et al. 2012), and antibodies to NR2 (Dickerson, Stallings, Vaughan, Origoni, Khushalani, and Yolken 2012). Of note, CRP is a non-specific marker of inflammation which is elevated in many individuals with schizophrenia and has been found to be reduced by the administration of a sulforaphane nutraceutical (Bahadoran et al. 2013). These measures will also be performed at visit 7 (week 10) and visit 11 (week 18).
- Blood sample (approximately 8 ml) used to measure levels of biomarkers of inflammation including Keap 1/Nrf2-induced markers of cytoprotection and of the heat shock response (in peripheral blood mononuclear cells), using real time PCR and protein gels (Western blots). These samples will be analyzed in the Johns Hopkins Cullman Chemoprotection

- Center of [name]. These measures will also be performed at visit 7 (week 10) and visit 11 (week 18).
- Blood sample (4-6 ml) for the measurement of the blood level of the antipsychotic medication. These measures will be performed also at visit 11 (week 18).
- Throat swab samples for study of the oropharyngeal microbiome. These measures will be performed at visit 2 (week 0), visit 7 (week 10), and visit 11 (week 18)
- Urine sample for compliance and dose potency testing. Sulforaphane-glutathione dithiocarbamate (DTC) metabolites will be measured from urine provided by participants as biomarkers of compliance. These tests will also be performed at the Johns Hopkins Cullman Chemoprotection Center. These measures will also be performed at visit 7 (week 10) and visit 11 (week 18).

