These blood, throat swab, and urine samples will be identified by participant number only when they are sent to the research laboratories at Johns Hopkins for analysis. The clinical investigators will be blind to these results of the participant's research laboratory tests during the course of the trial. The laboratory scientists will be blind to the participant's treatment assignment during the course of the trial.

Placebo Lead-In Phase

Participants will begin a 2 week single-blind placebo phase at visit 2 (week 0), within 7 to 30 days of completion of the screening visit. Visit 2 (week 0) will take approximately two to three hours to complete. Participants who complete the two week placebo run-in phase and continue to meet eligibility criteria will be randomized to a treatment arm at visit 3 (week 2).

Randomization and Double-Blind Treatment Phase

Double-blind randomization will occur at visit 3 (week 2). Participants will be randomized to receive either the sulforaphane compound or placebo tablets which are indistinguishable from the sulforaphane tablets for the 16 weeks of the double-blind phase. Symptom evaluations will be completed at bi-weekly study visits at which time participants will also be evaluated for adverse events. Visits 3 to 10 (weeks 2 to 16) will take approximately one hour each to complete. Visit 11 (week 18) will take approximately two to three hours to complete.

Randomization will assure that out of N=64 total participants, approximately half are assigned to each treatment arm. In addition, block randomization, based on initial PANSS total scores, will be used to assign participants to the two treatment groups to avoid differences in initial PANSS scores between the groups. Only the study data manager and the study pharmacist will be aware of participant assignment during the trial.

Treatment providers will be asked to maintain participants on the same psychotropic medication regime throughout the study. At each bi-weekly study visit, research staff will document any medication changes. Any medication changes that are made will be studied as a secondary outcome.

The study compound will be taken once per day and the dose will not be adjusted throughout the trial.

Visit Windows

Visit 2 (week 0) will take place 7 to 30 days after visit 1 (screening). Visits 3 to 11 (weeks 2 to 18) will take place 12 to 16 days after the previous visit. Visits may be divided into separate sessions to minimize participant fatigue.

Compliance

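### Nothing in the plan protects the stated laboratory blind for the Nrf2 and heat-shock markers: one center also receives the urine sulforaphane metabolites under the same participant number

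*Combined protocol and SAP*

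**What the plan says.** The relevant text is in section 5, under Research Laboratory Measures.

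- **Marker blood.** About 8 ml is drawn for "Keap 1/Nrf2-induced markers of cytoprotection and of the heat shock response", read by real-time PCR and Western blot. The text continues: "These samples will be analyzed in the Johns Hopkins Cullman Chemoprotection" Center. Sampling is at visits 2, 7 and 11.
- **Urine.** DTC metabolites of sulforaphane are measured at the same three visits, as a check on compliance and dose potency. "These tests will also be performed at the Johns Hopkins Cullman Chemoprotection Center".
- **Labelling.** "These blood, throat swab, and urine samples will be identified by participant number only" when shipped to Johns Hopkins.
- **Blinding.** "The laboratory scientists will be blind to the participant's treatment assignment during the course of the trial". Clinical investigators are separately kept from the research laboratory results while the trial runs. Under Randomization: "Only the study data manager and the study pharmacist will be aware of participant assignment during the trial".

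Section 7 compares the inflammatory biomarkers between groups over time (Aim 2) and by t-tests at initial and follow-up visits (Aim 3). Aim 2 in section 2 names heat shock protein 90.

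**The concern.** Withholding the allocation list blinds a laboratory only if nothing it measures gives the allocation away. Here one of the two assays measures what the body makes from the active ingredient. Anyone at the center who sees a participant's urine result can form a good guess at the arm, and the blood being read for that person carries the same number.

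This matters most for Western blots. Background subtraction, the decision to repeat a run and the rejection of an odd lane all call for judgment; this is a general property of the method, as the plan describes no blot procedure. If the blots were read with knowledge of the arm, a group difference in these markers could come from handling, and the mechanistic result would be hard to defend as blinded.

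**Working it through.** The plan states no figure on this point to reproduce. The check traces the samples first, then asks how informative the urine result is.

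**1. The sample path (section 5)**

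| | Nrf2 / heat-shock blood | Urine DTC |
|---|---|---|
| Laboratory | Cullman Chemoprotection Center | the same |
| Visits | 2, 7, 11 | 2, 7, 11 |
| Identifier | participant number | participant number |
| Withheld from | clinical investigators | clinical investigators |

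No text withholds the urine result from those who read the blood. No text gives the urine its own code, assigns different staff, or sets the order of the assays.

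**2. Why DTC points to the arm**

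- Section 2 describes DTC as the final urinary metabolites of sulforaphane.
- Section 5 calls dietary sulforaphane low, and users of broccoli supplements are excluded.
- Visit 2 comes before any active drug, so each participant has an off-drug reference.
- The plan itself relies on DTC to confirm intake of active tablets. A marker that can do that also separates active from placebo.

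**3. Expected separation**

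Inputs: 6 tablets per day at 37 µmol glucoraphanin each (section 5); conversion to urinary DTC at least 35%, expected about 40% (section 2).

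- Daily glucoraphanin: 6 × 37 = 222 µmol.
- DTC per 24 h: 222 × 0.35 = 77.7 and 222 × 0.40 = 88.8 µmol.
- If the percentage is applied instead to the approximately 100 µmol of sulforaphane: 100 × 0.35 = 35 and 100 × 0.40 = 40 µmol.

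The documents give no placebo background, so it is assumed here. Ratio = active ÷ background:

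| Assumed background (µmol per 24 h) | Base 222 µmol | Base 100 µmol |
|---|---|---|
| 1 | 77.7 to 88.8 | 35 to 40 |
| 10 | 7.8 to 8.9 | 3.5 to 4.0 |
| 20 | 3.9 to 4.4 | 1.75 to 2.0 |

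**4. Effect of missed doses**

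A participant is terminated after more than 32 missed doses, so 32 is the most allowed. Let m be the share missed: 32/126 = 25.4% over 18 weeks, or 32/112 = 28.6% over the 16 double-blind weeks. Assume that misses are independent, that a sample is positive when that day's dose was taken, and that placebo gives no false positives. Then P(positive at visit 7 or 11) = 1 − m², and with equal arms the share classified correctly = (1 + 1 − m²)/2.

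| m | One sample positive (1 − m) | At least one of two (1 − m²) | Correct arm, all participants |
|---|---|---|---|
| 10% | 90% | 99% | 99.5% |
| 25.4% | 74.6% | 93.5% | 96.8% |
| 28.6% | 71.4% | 91.8% | 95.9% |

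These figures are illustrations. They do not predict what one visit sample in this trial will read.

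**The case against.** **The blind may hold in practice.** A reader might infer that the blind must fail, or that the trial will report as blinded what is not. The documents do not support that. They do not say who runs each assay, when the urine is run, or whether urine results circulate within the center. With different staff, or DTC batched at the end, the sentence would be true, and laboratory procedures outside these documents may already provide for this. This stands: the supportable claim is that the plan states no protection.

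**The separation figures come from another setting.** The 35-40% conversion belongs to healthy volunteers who fasted, avoided cruciferous foods and collected all urine for 8 plus 16 hours. The trial asks for a urine sample at a visit, with no stated time since dose or collection period and no restriction on diet. This also stands, and rules out an exact classification rate. It does not remove the direction: a sample too uninformative to separate the arms would not serve as a compliance check either.

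**The consequence is not quantified.** A reader might attach a false-positive rate to the Aim 2 comparisons. Any such rate would only be the power of a test against an assumed handling shift, and nothing in the documents supports a particular shift.

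**The role of the laboratory's head.** Section 2 places the development of the DTC method in the laboratory of a study investigator. A reader might infer that an investigator would be the person unblinded. With names removed, the text does not establish who heads or reads which assay, and the point does not need it.

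**The scope is narrow.** Agreed. CRP, TNF alpha and the antibodies are listed separately and not assigned to this center, and real-time PCR is largely read by instrument.

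**Conclusion.** The concern holds in a limited form. As written, the plan lets one center link a result that largely reveals the arm to the marker samples it reads, and states nothing to prevent this. The laboratory blind, and the statement that only the data manager and pharmacist know assignments, are unprotected.

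This rests on the stated laboratory, visits and labelling rule, and on the plan's own account of DTC and of low dietary intake. How well DTC separates the arms in these samples cannot be fixed from the documents.

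Any bias would fall on the Aim 2 and Aim 3 markers read at this center, Western blots most of all, and its size is unknown. PANSS and MCCB are not measured there, and the clinical investigators do not see these results during the trial, so the primary outcome is not in question. It is worth correcting because the remedy is nearly free.

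**What to change.** In section 5, Research Laboratory Measures, adopt one of two procedures:

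1. Label the urine aliquots with a second code unrelated to the participant number. The key stays with the pharmacist or data manager, both already unblinded.
2. Store the urine and run DTC only after the PCR and Western blot data are final and locked.

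Then reword the blinding sentence to describe the procedure chosen.

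The first option costs a second set of labels and a linking file. The second delays the DTC and dose-potency results. That delay should not affect trial conduct: section 5 states no rule that uses DTC while the trial runs, counseling follows pill counts or participant reports, and the clinical investigators are not shown these results in any case.

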5. STUDY DESIGN AND PROCEDURES

Study Overview

Over a two year period, we will randomize N=64 participants who have residual psychotic symptoms which are of at least moderate severity. Based on our experience performing similar clinical trials, we anticipate that we will evaluate up to 100 participants in order to randomize 64. We expect a drop-out rate of 15% after randomization. The trial will begin with a 2 week singleblind placebo run-in phase followed by a 16 week double-blind phase. During the placebo run-in phase, participants will receive placebo 6 tablets once per day. During the double-blind phase, participants will receive either the sulforaphane tablet 6 tablets once per day (equivalent to ~100 umol of sulforaphane) or the placebo 6 tablets once per day. The primary outcome that will be assessed is the severity of psychiatric symptoms as measured by the Positive and Negative Syndrome Scale (PANSS) (Kay et al. 1987). We will also measure cognitive functioning with the MATRICS Consensus Cognitive Battery (MCCB) (Nuechterlein et al. 2008). In addition, we will study the effect of the sulforaphane compound in lowering several biomarkers of inflammation including C-Reactive Protein (CRP), heat shock protein 90, and other markers of inflammation and cell damage. We will also investigate the association between the efficacy of sulforaphane therapy and initial and follow-up levels of these markers. For a detailed list of procedures and assessments at each study visit, see the Schedule of Assessments.

Study Compound

The active study compound and identical-appearing placebo will be prepared and provided by Nutramax Laboratories, Edgewood, MD, USA, the company that makes Avmacol®, a commercially-available over-the-counter compound (http://www.nutramaxstore.com/avmacolreg-60-tablets-p430.aspx). The active ingredient in Avmacol® is produced naturally by extracting the biologically inactive glucosinolate, glucoraphanin, from broccoli seeds, and compressing it in tablets with active myrosinase from broccoli sprouts. The ingestion of this compound leads to the

hydrolysis of glucoraphanin and the generation of sulforaphane within the gastrointestinal (GI) tract and the subsequent systemic absorption of the sulforaphane.

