Pill counts and/or participant reports of compliance will be obtained. If pill counts or participant reports indicate the participant has not taken all of the prescribed study compound, the participant will be counseled about the importance of following directions. If the participant has missed more than 32 daily doses cumulatively throughout the study (>25% of study drug), the participant will be terminated from the study.

Compliance will also be confirmed with laboratory testing of urine samples provided by participants at 3 points during the trial (visits 2, 7, and 11). Participants will be told that these samples will be collected at random. These urine samples will be used to measure sulforaphane-glutathione metabolites in [name] laboratory.

Discontinuation

A participant may be discontinued from the study for any of the following reasons:

- If the participant fails to follow study directions (failure to keep appointments, follow directions or take the study compound as instructed)
- If the participant does not attend study visits, or is not in contact with research staff for 3 bi-weekly consecutive study visits
- If the participant has a positive drug screen, research staff will inform the participant that a repeat test will be done at the next visit; if the next test is positive then she/he will be removed from the study
- If it is the judgment of the study physician, in an effort to improve the participant's medical care, or if the participant develops a serious medical illness, becomes pregnant, or begins breast feeding
- If the participant has unexpected or serious side effects or serious medical complications

If a participant discontinues from the study, discontinuation assessments will be done at the discretion of the principal investigator.

A participant may withdraw from the study at any time at his/her own request.

Clinical Outcome Measures

• The primary outcome measurement will be the change in scores on the Positive and Negative Syndrome Scale (PANSS) (Kay et al. 1987) from the beginning to the end of the double-blind treatment phase, visits 3 to 11 (weeks 2 to 18). The PANSS contains 30 items that assess symptoms of schizophrenia including positive, negative and general symptom psychopathology. The PANSS was chosen because of its widespread use in clinical studies of psychosis and its demonstrated reliability in assessing psychopathology across diverse patient populations.

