7. STATISTICAL ANALYSIS

Power calculations indicate that a sample size of N=64 has 80% power to find an effect size of d = .76 with an alpha = .05 and a two-tailed test of change between groups from screening to end of study.

Aim 1: Safety data will be analyzed using incidence density analysis, to compare rates of adverse events across groups, as well as survival analysis, to assess group differences in retention. PANSS total scores will be the primary efficacy endpoint. Repeated-measures regression models will be used to assess the main effects of group and time, plus the time by group interaction. This method is able to utilize all available data from participants with

incomplete follow-up, thus including participants who drop out of the study. (Based on our experience in previous trials with this population, we anticipate attrition of about 15% over the course of the trial.) A similar analytical approach will be used for the PANSS subscales and the MCCB outcome measures.

Aim 2: Repeated measures regression modeling will also be used to evaluate the effect of medication group, time, and their interaction on inflammatory biomarkers.

Aim 3: Treatment groups will be compared with respect to initial and follow-up levels of inflammatory biomarkers using *t*-tests. If groups are found to differ in this regard, the efficacy analyses will be repeated, adding the initial biomarker levels as covariates in the model.

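### The visit 2 PANSS is scheduled before randomization but given no role in the primary analysis; adding it as a second baseline covariate would cost little and may gain precision

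*Combined protocol and SAP*

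**What the plan says.** - **Schedule.** Section 9 (Schedule of Assessments) marks the PANSS at all eleven visits, including screening, visit 2 (start of the placebo run-in) and visit 3.
- **Randomization.** Section 5 (Randomization and Double-Blind Treatment Phase): "Double-blind randomization will occur at visit 3 (week 2"). Visit 2 therefore precedes assignment for every participant.
- **Primary outcome.** Section 5 (Clinical Outcome Measures) takes PANSS change "from the beginning to the end of the double-blind treatment phase, visits 3 to 11 (weeks 2 to 18").
- **Model.** Section 7, Aim 1: "Repeated-measures regression models will be used to assess the main effects of group and time, plus the time by group interaction". It gives no list of visits, PANSS baseline covariate, covariance structure or named test contrast. The only covariate mentioned for the efficacy models is the initial biomarker level, and that is conditional on a group difference.
- **Sample size.** Section 7 states that a "sample size of N=64 has 80% power" for an "effect size of d = .76 with an alpha = .05 and a two-tailed test", and describes this as a "two-tailed test of change between groups from screening to end of study".

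**The concern.** A single PANSS rating carries rater error and short-term fluctuation. When change is measured from one rating, all of that noise enters the change score. A second rating taken two weeks earlier, which assigned treatment cannot affect, helps to separate a participant's usual level from the noise. The plan collects this rating and does not say what to do with it.

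Adjusting for visit 3 alone would not settle the matter, because visit 2 can still carry information that visit 3 lacks. The trial is sized for a large effect with little reserve once attrition is counted, so precision from data already scheduled is worth having. The choice also needs to be made in advance: picking a baseline after seeing results invites the charge of selection.

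**Working it through.** **Inputs from the documents.** N = 64, 80% power, d = .76, two-sided alpha .05 (section 7). About 1:1 allocation: "approximately half are assigned to each treatment arm" (section 5). Attrition: "We expect a drop-out rate of 15% after randomization" (section 5).

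**Assumptions.** The documents give no correlation between PANSS ratings, so a range is shown. Variance is set to 1 at each visit, and the visit 3 rating is taken to precede the first dose of assigned treatment.

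**Step 1: the plan's own figure.** 64 × 0.85 = 54.4, or about 27 completers per arm. A two-sample comparison at d = .76 then has power 79.7% (normal) or 78.2% (noncentral t), close to the stated 80%. With all 64 (32 per arm) it is 86.0% or 84.9%, which does not match. The stated figure therefore fits a completers calculation, although section 7 does not say so.

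**Step 2: formulas.** Let a = corr(visit 3, visit 11), b = corr(visit 2, visit 11) and c = corr(visit 2, visit 3). The residual variance at week 18 is:

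- visit 3 covariate only: V1 = 1 − a²
- visits 2 and 3 as separate covariates: V2 = 1 − (a² + b² − 2abc)/(1 − c²)

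The gain from visit 2 is 1 − V2/V1.

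**Step 3: compound symmetry (a = b = c = r).** V2 reduces to 1 − 2r²/(1 + r).

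| r | V1 | V2 | V2/V1 | cut |
|---|---|---|---|---|
| .5 | .750 | .667 | .889 | 11% |
| .6 | .640 | .550 | .859 | 14% |
| .7 | .510 | .424 | .830 | 17% |
| .8 | .360 | .289 | .802 | 20% |

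To express this as power, take 27 per arm and d = .76 on the SD of the visit 3 to 11 change. At r = .7 the change-score variance is 2(1 − .7) = .60. Power is 78.2% for the raw change score, 84.4% adjusting for visit 3, and 90.3% adjusting for both. More than half of the rise (6.2 of 12.1 points) comes from adjusting for visit 3 at all.

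**Step 4: serial correlation plus rating error.** Variance is split into a stable part, an AR(1) part (.85 per two-week step) and independent error.

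| stable / serial / error | c | a | V1 | V2 | cut |
|---|---|---|---|---|---|
| .5 / .3 / .2 | .755 | .582 | .662 | .622 | 6.0% |
| .4 / .4 / .2 | .740 | .509 | .741 | .711 | 4.0% |
| .3 / .5 / .2 | .725 | .436 | .810 | .789 | 2.6% |

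Other plausible splits widen this to about 2% to 8%.

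**Step 5: pure AR(1), no rating error.** Here b = ac, so visit 2 adds nothing once visit 3 is known. At .95 per step, V1 = V2 = .560 and the cut is 0%.

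**Step 6: averaging visits 2 and 3.** Under compound symmetry the change-score variance falls from 2(1 − r) to 1 + (1 + r)/2 − 2r = 1.5(1 − r), a 25% cut at any r. Under pure AR(1) it can rise: from .673 to .681 (+1.2%) at .95 per step, and from .298 to .305 (+2.4%) at .98. Used as a single covariate, the mean is worse than visit 3 alone by 2.0% and 2.6% in the same two cases.

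**Step 7: which contrast benefits.** A covariate main effect is constant over time within a participant. With complete data it shifts each participant's level and leaves a linear group-by-time slope, and its standard error, essentially unchanged. The gain in steps 3 and 4 belongs to the between-arm difference at a given visit, with the covariate effect free to vary by visit. Likewise, adding visit 2 only as another unconstrained time level under unstructured covariance would not sharpen the visit 3 to 11 contrast.

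**The case against.** The strongest reply is that this is an analyst's preference. The plan contains no bias here, and section 7 leaves room for visit 2: it lists no visits, and its power sentence even refers to change from screening. A reader might infer that the plan excludes visit 2 from every model. The text does not support that; it only specifies no use of it.

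The reply also has force on size. Compound symmetry treats ratings two weeks apart as no more alike than ratings sixteen weeks apart, which favours the proposal. Under serial correlation the gain is small and can vanish. The calculation is also for a week 18 comparison, whereas section 7 names a group-by-time interaction without saying which contrast is tested. If that is a linear slope, a visit 2 main effect does not help.

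Averaging the two baselines is open to further objection. It would depart from section 5, which measures change from the start of double-blind treatment, by mixing in a rating from the start of the placebo run-in. It can also lose a little precision.

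These points limit the size of the claim and shape the remedy. They do not remove the point: with two separate covariates, the known cost is about one degree of freedom, and the data are already scheduled.

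**Conclusion.** The point stands as an efficiency improvement. The visit 2 PANSS is pre-randomization and scheduled for everyone, and no analysis role is specified for it. Beyond a visit 3 covariate, the cut in week 18 residual variance is 11% to 20% under compound symmetry (r = .5 to .8), about 2% to 8% with serial correlation plus rating error, and 0% under pure AR(1). A rater-scored scale with no rating error is an extreme case, so some gain is likely, but the documents cannot fix its size.

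Two stronger readings should be resisted. One is that the trial forgoes a gain worth about 20% more participants (.510/.424 ≈ 1.20). That is the compound-symmetry result at r = .7 and rests wholly on that assumption. The other is that the primary comparison is invalid or biased without visit 2. Nothing in the documents supports this, since randomization protects the between-arm comparison either way.

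**What to change.** In section 5 (Clinical Outcome Measures) and section 7 (Aim 1):

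1. State that the outcomes modelled are PANSS totals at visits 4 to 11.
2. Enter visit 3 and visit 2 PANSS totals as separate pre-randomization covariates, each allowed to interact with time. Equivalently, include visits 2 and 3 as outcome levels with arm means constrained equal.
3. Name the between-arm difference at week 18 (visit 11) as the primary contrast.
4. Keep visit 3 as the stated baseline for change; do not replace it by the mean of visits 2 and 3.
5. Align the power sentence, which refers to change from screening, with the named baseline.

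The cost is a few lines of text and about one degree of freedom, or a few more with the time interactions. It needs no new data, visits or participants.
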